## L.2.2 Major Adverse Events (MAEs)

Respiratory complications	
Atelectasis	
Collapse of part or (much less commonly) all of a lung caused by a blockage of the air passages (bronchus or bronchioles) or by pressure on the outside of the lung.
 
Clinical evidence of atelectasis is determined by physical, radiographic, and laboratory findings requiring treatment with antibiotics, inhalation therapy, intubation, or suctioning.

Pneumonia	
Inflammation of the lung, usually caused by an infection.
 
Clinical evidence of pneumonia is determined by physical, radiographic, and laboratory findings requiring treatment with antibiotics, inhalation therapy, intubation, or suctioning.

Pulmonary embolism	Sudden onset of pleuritic chest pain, cough, hemoptysis, hypoxia, tachycardia and a positive ventilation/perfusion (V/Q) scan.
Pulmonary edema	Abnormal accumulation of fluid in the lungs.
Respiratory failure	The need for ventilatory support for >72 hours associated with an inability to wean from the respirator for any reason.
Renal complications	
Renal failure	Sudden reversible failure of renal function caused by shock, interruption of blood flow to the kidneys, direct damage to the kidney's and/or sudden obstruction of urine flow.
Renal insufficiency	Slowly progressive failure of renal function resulting from some disease (e.g., diabetes, cancer, hypertension, glomerulonephritis) that causes gradual destruction of the kidneys or if creatinine levels are available, an increase of >25% above the pre-procedure creatinine level.
Cardiac complications	
Myocardial Infarction (MI)	
 
Non-Q-wave MI is defined as elevated CK > 2X the upper lab normal with the presence of elevated CK-MB (any amount above the institutions upper limit of normal) in the absence of new pathological Q waves.
 
Q wave myocardial infarction is defined as development of new, pathological Q waves in 2 or more contiguous leads (as assessed by the ECG core laboratory) with post-procedure CK elevation >2x ULN and CKMB levels elevated above normal.
 

Unstable angina	Chest pain unrelieved by anti-anginal medications in a subject with known coronary artery disease without significant elevations in cardiac enzymes.
New arrhythmia	The development of new atrial arrhythmia, new ventricular arrhythmia, exacerbation of a prior arrhythmia, a significant increase in severity of a current arrhythmia or any episode of cardiac arrest.
Congestive Heart Failure (CHF)	Failure of the heart to pump blood with normal efficiency. Development of an acute episode of or exacerbation of existing low cardiac output or fluid overload accompanied by peripheral and/or pulmonary edema.

Central and peripheral neurological complications	
Cerebrovascular accident (CVA) / Stroke	Defined as sudden onset of vertigo, numbness, aphasia, or dysarthria due to vascular lesions of the brain such as hemorrhage, embolism, thrombosis, or rupturing aneurysm, that persisted >24 hours.
Cerebrovascular Embolic event	The obstruction of a blood vessel from the brain by a blood clot or foreign substance (e.g. air, fat, bacteria).
Paraplegia	Complete loss of motor function in the lower extremities and lower portions of the trunk. A thoracic or lumbar injury can affect leg, bowel and bladder control and sexual function.
Paraparesis	Mild loss of bilateral lower extremity motor function; bilateral lower extremity weakness.
Gastrointestinal complications	
Bowel ischemia	A decrease in blood supply to either the large or small intestine that is associated with pain, bleeding, abdominal distension, diarrhea or x-ray or angiographic evidence of reduced organ flow.
Major Bleeding complications	
Bleeding, procedural	A blood loss greater than 750 cc occurring before the subject leaves the OR.
Bleeding, post-procedural	Post-procedural bleeding greater than 750cc occurring after the subject leaves the OR.
Coagulopathy	The development of an abnormal bleeding disorder (e.g., Disseminated Intravascular Coagulopathy or Thrombocytopenia with platelet counts of < 80,000) documented by appropriate laboratory studies requiring therapy with medication or transfusion.
Vascular complications	
Aortic rupture	The tearing apart of the aortic tissue. Signs of aortic rupture include hemothorax, unrelenting chest or back pain, or hypotension refractory to medical management for a period exceeding two (2) days.
Aneurysm rupture	See definition of Thoracic Aortic Aneurysm rupture in section L.2.1
Hematoma at access site	An abnormal localized collection of blood (clotted or partially clotted) and situated at level of access site(s) used for endovascular procedure.
Pseudo or false aneurysm	Enlargements of the aorta, iliac or femoral arteries, which contain some or all of the medial layer, the adventitia, and periaortic tissue; most commonly associated with previous aortic operative procedures, trauma, and/or infection. Pseudo-aneurysms typically present as a well-defined collection of blood outside the vessel wall from contained rupture.
Arteriovenous (AV) fistula	Formation of an abnormal connection between the lumens of an artery and a vein as documented by CT, ultrasound, angiography or direct observation.
Retroperitoneal bleed	Bleeding into the retroperitoneal space due to trauma, surgery or percutaneous puncture of an artery or vein.
Limb ischemia	A decrease in blood supply to either the inferior or superior limb(s).
Thrombosis	Clotting within a blood vessel which may cause infraction of tissues supplied by the vessel; it may be occlusive or attached to the vessel or heart wall without obstructing the lumen.

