## F.6 Adverse events

### F.6.1 Definition/classification

For the purposes of the clinical report, Medtronic will classify each Adverse Event according to ISO 14155:2011.\* In case country specific definitions and safety reporting regulations are stricter than mandated per ISO 14155:2011, reporting will be done in compliance with the country specific safety regulations.

All adverse events that meet the study definitions will be reported to the sponsor and documented on the Adverse Event eCRF and in the subject’s medical records.

Clinical events that are inherent to a surgical procedure and expected to occur in the majority of subjects for a projected duration may be considered unavoidable. Such events are listed in Table F-3. These events should not be to be reported as adverse events during this study.

\*: For example, the definition of Serious Adverse Event (SAE) in Germany per the MPSV, § 2 nr 5 is the following:

Serious adverse event is any adverse event, which occurs in an approved clinical investigation or performance evaluation and which has led, might have led or could lead directly or indirectly to the death or any serious deterioration in the state of health condition of a subject, a user or any other person without considering if the event has been caused by the medical device.

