#### *I.2.4 Imaging Core Lab*

An imaging core lab will be established to independently analyze images based on the imaging protocol/core lab guidelines. Imaging guidelines will be provided in the investigational site file.

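### Four MAE definitions in Appendix L.2.2, read as written, exclude or misfile real events; one depends on an ECG core laboratory the protocol does not set up

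*Protocol*

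**What the plan says.** MAEs are listed among the secondary endpoints at 30 days and at 12 months (protocol C.2.2.1 and C.2.2.2). C.2.2.1 refers to Appendix L.2.2 for their definitions. Four entries there matter here.

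- **Stroke:** "Defined as sudden onset of vertigo, numbness, aphasia, or dysarthria due to vascular lesions of the brain". Several causes are named as examples, but the four symptoms are not introduced as examples. The deficit must also outlast 24 hours. A neighboring entry, cerebrovascular embolic event, covers "The obstruction of a blood vessel from the brain by a blood clot or foreign substance" and sets no symptom or duration test.
- **Pulmonary embolism:** "Sudden onset of pleuritic chest pain, cough, hemoptysis, hypoxia, tachycardia and a positive ventilation/perfusion (V/Q) scan".
- **Renal failure:** "Sudden reversible failure of renal function caused by shock", followed by other acute causes. The companion entry, renal insufficiency, describes slowly progressive disease or, where creatinine is available, a rise of more than 25% over the pre-procedure value.
- **Q-wave MI:** new pathological Q waves "as assessed by the ECG core laboratory", with raised cardiac enzymes. The non-Q-wave entry requires that no new pathological Q waves are present.

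The only core laboratory the protocol creates is in I.2.4: "An imaging core lab will be established to independently analyze images". SAP section 7.9 cites L.2.2 for the MAE definitions. It then says MAEs will be identified from MedDRA codes supplied by the sponsor's safety group. The list is not given, and the SAP does not say which source prevails.

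**The concern.** A definition should admit the event it names. Read literally, each of these entries turns away a recognizable form of its own event. The Q-wave MI entry adds a condition that cannot be satisfied with the bodies the protocol sets up. No stated safeguard corrects a literal reading: the CEC remit in F.6.6 covers MDEs, deaths and DTAA ruptures and does not name MAEs, although its charter, which is not shown, may add selected events.

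What is at stake is the MAE count and its split by component. With 47 subjects and few events expected in any one component, a single missed or misplaced event visibly changes what is reported.

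**Working it through.** There is no planned MAE rate to reproduce, so the main check sets the entries against one another. Each case below is an event that has occurred and been recorded.

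| Event | Its own L.2.2 entry | Other MAE entry that might take it | Result |
|---|---|---|---|
| Q-wave MI read on the site ECG | Not met: core-laboratory reading required | Non-Q-wave MI: not met, new Q waves are present | Meets neither MI entry |
| Embolic stroke, motor deficit only | Not met | Cerebrovascular embolic event | Counted, under another neurological entry |
| Thrombotic stroke, motor deficit only | Not met | Thrombosis (vascular) | Probably counted, but not as neurological |
| Hemorrhagic stroke with only motor, visual or consciousness deficit | Not met | None for stroke | Not counted |
| Stroke fatal within 24 hours | Not met: duration test | As above, by cause | Counted as a death; as an MAE only if embolic or thrombotic |
| PE proven by contrast CT, no V/Q scan | Not met | Possibly thrombosis | Not in the respiratory component |
| Sudden permanent renal failure | Not met: must be reversible | Renal insufficiency, if creatinine is available | Misfiled, or lost without creatinine |

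Three checks on feasibility:

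- Contrast CT/MRI is the scheduled imaging in Tables F-2 and L-2, so a CT diagnosis of PE is a realistic route that the PE entry does not accept.
- Neither table schedules a creatinine test, so the renal fallback depends on routine care.
- Neither table schedules an ECG. F.5 lists laboratory results and ECG reports among source records, so both may exist for individual subjects.

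Other entries are more open. AV fistula accepts several imaging methods or direct observation, and loss of patency (L.2.1) accepts any appropriate modality. The narrowness is therefore not a consistent policy of the appendix.

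**Scale.** Inputs: n = 47 (protocol C.7) and 100 for the pooled set (SAP section 6). The change in a rate per missed subject is 1/n.

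- This trial: 1/47 = 2.1 percentage points.
- Pooled set: 1/100 = 1.0 point.

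Exact (Clopper-Pearson) two-sided 95% limits for 47 subjects, which agree with Table C-1:

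- 0 events: 0% to 7.5%
- 1 event: 0.1% to 11.3%
- 2 events: 0.5% to 14.5%

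Reporting 0 instead of 1 thus moves the upper limit from 11.3% to 7.5%. Reporting 1 instead of 2 moves it from 14.5% to 11.3%. A component rate moves by 1/n for every missed event. The overall MAE rate moves only when the subject has no other MAE. SAP Table 5 restricts the 12-month denominator, so with dropout the step there is somewhat larger than 2.1 points.

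**The case against.** The strongest reply is that nothing is lost from the safety record. F.6.2 requires every AE outside Table F-3 to be reported, whatever its relatedness or outcome, and an Independent Medical Monitor reviews all events. A reader might take the sentence in F.6.1, "All adverse events that meet the study definitions will be reported to the sponsor", to mean that events failing L.2.2 go unreported. F.6.2 does not support that reading. Deaths count under mortality and go to the CEC.

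A second reply is that the SAP works from MedDRA codes, so a CT-proven PE or a stroke with hemiparesis coded to its own term could count despite L.2.2. This is fair, and it means a reader should not infer that the reported MAE rate is demonstrably too low. It does not remove the defect. If L.2.2 governs, events are excluded or misfiled; if the codes govern, the reported MAEs do not match their stated definition. The SAP is written mainly for the US trial and cites an Appendix L.5 that this protocol lacks, so its reference to L.2.2 may be to the US protocol.

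Third, it is tempting to conclude that strokes in general are lost, or that the main safety endpoint is compromised. The documents support neither. The embolic-event and thrombosis entries can hold many ischemic strokes. MAEs sit in an unranked list of secondary endpoints, for which SAP 7.9 plans no inferential analysis. Both renal entries are MAEs, so with creatinine available the overall count is unchanged.

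**Conclusion.** The point holds as a defect in four definitions. As written:

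- a Q-wave MI meets neither MI entry;
- a hemorrhagic stroke without any of the four listed symptoms meets no MAE entry for stroke;
- a CT-proven PE fails the PE entry;
- sudden permanent renal failure is at best filed as renal insufficiency.

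The effect is confined to MAE counts and component categories, which are descriptive. It is 2.1 points for each subject in 47 whose only MAE is missed. AE and SAE reporting, mortality, the primary endpoint and its sample size are not affected.

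The size of any undercount is unknown. The documents give no rates for stroke, PE, renal failure or MI, and the MedDRA list is not shown. The conclusion assumes that L.2.2 is applied as worded. That a stroke may present with motor, visual or consciousness deficit alone is general clinical knowledge and is not stated in the documents; the omission itself is in the text. The change is worth making because it is cheap and one criterion cannot be met at all.

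**What to change.** Edit four entries in L.2.2:

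- **Stroke:** any new focal or global neurological deficit of vascular origin, including motor, visual or consciousness deficit, lasting more than 24 hours or leading to death.
- **Pulmonary embolism:** confirmed by CT angiography, V/Q scan, angiography or autopsy, without requiring every listed symptom.
- **Renal failure:** delete the word reversible and report separately whether the failure resolved.
- **Q-wave MI:** read Q waves from the site ECG instead of a core laboratory.

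State in SAP 7.9 that the MedDRA list must match these definitions, and align the US protocol so that pooled rates mean the same thing. Apply the revised definitions to AEs already collected, which F.6.2 makes feasible.

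The cost is a protocol amendment with the approvals F.8.3 requires, reclassification of some recorded events, slightly higher MAE rates, and less exact comparability with studies that used the current wording. No new test or committee is needed.

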### L.2.3 Device Deficiencies

As defined in section F.6.1, every Device Deficiency will be reported by the Investigator on a Device Deficiency Form regardless it resulted in an Adverse Event.

[figure not shown]
#### Listing of Device Deficiencies (DD) available in CRF drop down list

Implant procedure-specific DD	Inadequate labeling
	Inadequate packaging
	Use Error (specify : Not following IFU deployment steps, Not following IFU bailout technique instructions, Use of a device with an identified malfunction)
	Access Failure
	Insertion Failure
	Delivery Difficulty
	Delivery Failure
	Deployment Difficulty
	Deployment Failure
	Difficulty to release tip capture
	Failure to release tip capture
	Difficulty to remove delivery system
	Failure to remove delivery system
	Delivery system component breakage (e.g., handle, sheath, tip, etc.)
	Stent graft Incomplete Deployment (device does not fully deploy in target area)
	Misaligned Deployment
	Stent graft Infolding
	Incomplete apposition/mal-apposition of proximal stent with aortic wall (bird beak)
	Stent graft Improper placement (Misplacement) related to marker interpretation, improper manufacturing, physician error
	Any other failure/malfunction of Delivery System during procedure, specify: _____
Other DD:	Use Error – Inappropriate device over sizing
	Use Error – Inappropriate device overlap
	Use Error – Other, specify: _____
	Incomplete sealing, not due to anatomy or disease progression
	Stent graft Fabric porosity, not due to subject's heparinization or other anticoagulant medication
	Stent graft Fabric defect (specify: stent graft rupture, stent graft extrusion/ erosion)

	Stent graft Fracture (Specify: proximal bare stent, support spring, body stents, wireform)
	Stent graft Kinking*
	Stent graft Twisting*
	Stent graft Dilatation
	Stent graft Migration
	Stent graft Component Separation
	Stent graft Wire Detachment from Fabric (specify location)
	Any other failure/malfunction of Stent graft, specify: _____

\* Not intentional and not due to anatomy or disease progression

### L.2.4 Additional Definitions

Term	Definition
Landing zones of the thoracic aorta	 
The landing zones in the aorta for endovascular stenting are defined as follows:
 
Zone 0 – the proximal edge of the covered endograft lies proximal to the distal end of the innominate artery
 
Zone 1 – from distal end of the innominate artery to the distal end of the left common carotid artery
 
Zone 2 – from the distal end of the left common carotid artery to the distal end of the left subclavian artery
 
Zone 3 – from the distal end of the left subclavian artery to the end of the aortic arch curvature (<math>\leq 2</math> cm of the left subclavian artery without covering it)
 
Zone 4 – proximal extent of the endograft is <math>>2</math> cm distal to the left subclavian artery and ends within the proximal half of the descending thoracic aorta (T6 approximating the midpoint of the descending thoracic aorta)

## L.3. Investigational Plan Extension of Follow-Up Requirements

### L.3.1 Background

The purpose of this appendix is to describe the update to the Valiant Evo International Clinical Trial requirements increasing subject follow-up requirements to 60 months (5 years).

### L.3.2 Rationale

The reason for the proposed change is to better understand the long-term safety and effectiveness of the Valiant Evo Thoracic Stent Graft System in subjects with a DTAA. The extension of clinical follow up requirements provides longer-term evidence on the device's performance beyond the original 12-month term planned in the study, permitting accumulation of additional device use experience and clinical outcomes to support the marketing application and post-marketing surveillance.

The clinical evidence collected as part of this expanded follow-up period will be used in conjunction with the data collected from the concurrently enrolling Valiant Evo US Clinical Trial to support commercial approvals in geographies worldwide.

### L.3.3 Study Plan

#### L.3.3.1 Secondary Endpoints at 24, 36, 48 and 60 months

Secondary endpoints are to be assessed beyond 12 months. The following secondary endpoints are to be evaluated at 24, 36, 48, and 60 months:

- All-cause mortality
- Aneurysm-Related Mortality
- MDEs
- All AEs and SAEs
- Secondary procedures
- Loss of stent graft patency based on site reported imaging findings
- Endoleaks based on site reported imaging findings
- Stent graft migration as compared to 1-month imaging
- Aneurysm expansion > 5mm based on site reported imaging findings relative to the 1-month visit

Health-related quality of life outcomes are to be assessed at all scheduled follow-up visits using the EQ-5D questionnaire.

#### L.3.3.2 Subject accountability

Subjects already enrolled and willing to extend their follow-up from 12 to 60 months are to be re-consented. Re-consenting is to occur at or prior to the 12-month follow-up visit. Enrolled subjects who decline to continue to participate in follow-up beyond 12-months shall exit the study upon the completion of their 12-month visit.

#### L.3.3.3 Study duration

Subjects are followed under this investigational plan up to 60-months post-implantation. Subjects have additional follow-up evaluations at the following time points:

- 24-months following the index procedure
- 36-months following the index procedure
- 48-months following the index procedure
- 60-months following the index procedure

A Data Monitoring Committee and Clinical Events Committee continue to evaluate the subject health status and device performance and identify any safety concerns regarding subjects' well-being. An imaging core lab is not used to perform independent imaging assessments regarding device performance beyond 12 months of follow-up.

### L.3.3.4 Number of investigational sites and study duration

The total enrolment for this study will not exceed 47 patients in up to 17 sites, as originally mentioned in section C.7

The total enrollment period is expected to be approximately 30 months. Enrolled subjects are followed up at 1, 12, 24, 36, 48 and 60-months post-implantation.

### *L.3.4 Study preparation procedures*

#### L.3.4.1 Revisions in Informed Consent form

Medtronic revised the written informed consent template based on the changes contained within this appendix. Subjects who are currently participating in the study shall be asked to sign the updated informed consent to confirm their continuing informed consent in writing for up to 5 years of follow-up. Those subjects who have exited the study, or are lost for follow-up, are not contacted for study reasons again and are not re-consented to participate in follow-up beyond 12 months.

The revised informed consent documents are provided to the investigational sites for approval by the EC/IRB and or CA, as applicable by local regulations.

### *L.3.5 Study Methods*

#### L.3.5.1 Follow-Up Visits and Procedures

Subjects require post-implantation follow-up visits at 30-days, 12, 24, 36, 48 and 60 months. Follow-up visits and associated timeframe windows are summarized in Table L-1:

**Table L-1: Post-Implantation Follow-Up Visit Schedule and Windows**

Follow-Up Visit	Window Start Day	Target Day	Window Close Day
1 Month ( $\pm 15$ days)	15	30	45
12 Months ( $365 \pm 60$ days)	305	365	425
24 Months ( $730 \pm 60$ days)	670	730	790
36 Months ( $1095 \pm 60$ days)	1035	1095	1155
48 Months ( $1460 \pm 60$ days)	1400	1460	1520
60 Months ( $1825 \pm 60$ days)	1765	1825	1885

At all required follow-up visits subjects will undergo the following assessments and procedures:

- Physical Examination
- Chest CT/MRI with contrast
- EQ-5D questionnaire
- Adverse event assessment

#### L.3.5.2 Data collection requirements

The data collection schedule is summarized in Table L-2. Imaging source data is to be sent to a core lab for analysis up to the 12-month follow-up visit. Imaging source data beyond 12-months post-index procedure is not to be sent to the core lab for analysis. Instead, study sites are to report the results of the imaging performed as standard of care and in line with local and site

requirements directly on the e-CRF. Routinely acquired images may be required for adjudication purposes in case of CEC adjudication or any other safety event.

